Cycle 1:

Ublituximab			Umbralisib	Acalabrutinib
Day 1	Day 2	Day 8 & 15	Daily	Every 12 hours
150 mg	750 mg	900 mg	800 mg	previously tolerated dose

[figure not shown]
Cycles 2 through 6:

Ublituximab	Umbralisib	Acalabrutinib
Day 1	Daily	Every 12 hours
900 mg	800 mg	previously tolerated dose

Cycles 7-24:

Ublituximab	Umbralisib	Acalabrutinib
Day 1 of Cycles 9, 12, 15, 18, 21 and 24	Daily	Every 12 hours
900 mg	800 mg	previously tolerated dose

Study Schema - Re-Treatment

*Progression Of Disease (PD) – Defined per the iwCLL Criteria (Hallek 2018)

U2 – ublituximab and umbralisib; IB – ibrutinib; ACALA – Acalabrutinib; VEN – venetoclax; MRD – minimal residual disease; EOS – end of study

Retreatment will start with 2 cycles of single agent treatment with ibrutinib, acalabrutinib or venetoclax per the subject's history on study. Umbralisib and ublituximab will be started in Cycle 3 of re-treatment. Subjects will again be evaluated with serial peripheral blood MRD analysis. If subjects achieve U-MRD status in the peripheral blood, MRD will again be assessed by peripheral blood 4 weeks later to confirm U-MRD. Retreatment will continue until the occurrence of confirmed U-MRD response in the peripheral blood, completion of 26 cycles (24 cycles of triplet therapy), definitive disease progression, unacceptable toxicity, or withdrawal from the study due to investigator decision or other reasons. Subjects who discontinue study treatment and have not progressed will continue to be followed for disease progression.

Re-treatment schedule as follows:

Cohort A: Ublituximab and Umbralisib with Ibrutinib

Cycles 1 and 2:

Ibrutinib				
Daily				
Daily at previously tolerated dose. Investigator discretion may be used to start subjects at a higher dose than last tolerated (maximum dose 420mg daily).				

Cycle 3:

Ublituximab			Ibrutinib	Umbralisib
Day 1	Day 2	Day 8 & 15	Daily	Daily
150 mg	750 mg	900 mg	At appropriate dose based on initial protocol treatment	Previously tolerated dose. Investigator discretion may be used to start subjects at a higher dose than last tolerated (maximum dose 800mg daily).

Cycles 4 through 8:

Ublituximab	Ibrutinib	Umbralisib
Day 1	Daily	Daily
900mg	At appropriate dose based on previous Cycle	At appropriate dose based on previous Cycle

Cycle 9 through Cycle 26:

Ublituximab	Ibrutinib	Umbralisib
Day 1 of Cycle 11, 14, 17, 20, 23 & 26	Daily	Daily
900 mg	At appropriate dose based on previous Cycle	At appropriate dose based on previous Cycle

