5.4 RETREATMENT PHASE

Study Schema for Re-Treatment

*Progression Of Disease (PD) – Defined per the iwCLL Criteria (Hallek 2018)
U2 – ublituximab and umbralisib; IB – ibrutinib; ACALA – Acalabrutinib; VEN – venetoclax; MRD – minimal residual disease; EOS – end of study

Subject on treatment-free observation who subsequently develop clinical progression requiring treatment per iwCLL criteria (Hallek, et al., 2018) after 6 months of treatment-free observation will be retreated with the triple combination regimen that was previously received. Subjects who progress within 6 months of treatment-free observation discontinue from the study.

For subjects enrolled in Cohort A, retreatment will consist of 2 cycles of ibrutinib followed by treatment with ublituximab and umbralisib with ibrutinib cycles 3 through 26 of retreatment. The previously tolerated ibrutinib dose should be considered but is at investigator discretion (maximum dose 420mg daily).

For subjects enrolled in Cohort B, venetoclax should be initiated per the package insert. The target ramp-up dose should be considered based on the previously tolerated dose but is at investigator discretion (maximum dose 400mg daily). Retreatment will consist of 2 cycles of venetoclax followed by treatment with ublituximab and umbralisib with venetoclax cycles 3 through 26.

For subjects enrolled in Cohort C, retreatment will consist of 2 cycles of acalabrutinib followed by treatment with ublituximab and umbralisib and acalabrutinib cycles 3 through 26 of retreatment. The previously tolerated acalabrutinib dose should be considered but is at the investigator discretion.

Clinical response and U-MRD rate will be studied upon retreatment. If subjects achieve U-MRD status in the peripheral blood, MRD will be assessed by peripheral blood 4 weeks later to confirm U-MRD. Retreatment will continue until the occurrence of confirmed U-MRD response in the peripheral blood, completion of 26 cycles (24 cycles of triplet therapy), UTX-TGR-208

Version 2.0 Dated: 30 July 2020

definitive disease progression, unacceptable toxicity, or withdrawal from the study due to investigator decision or other reasons. Subjects who discontinue study treatment and have not progressed will continue to be followed for disease progression.

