7.3 STUDY ASSESSMENT AND TREATMENT SCHEDULE – RE-TREATMENT

Cycle=28 days	Screen	Cycle 1 ¹				Cycle 2 ²		Cycle 3 ³				Cycles 4-8 ⁴		C11-C26 ⁵	EOS ⁶	LTFU
Procedures/Days	D-28 to D1	D1	D8 ⁶	D15 ⁷	D22 ⁷	D1	D8 ⁷	D1	D2	D8	D15	D1	D1 every 3 Cycles			
Physical Examination	X	X				X		X				X	X	X		
ECOG PS	X	X				X		X				X	X	X		
Vital Signs ⁸	X	X	X	X	X	X	X	X	X	X	X	X	X	X		
12-Lead EKG	X															
Hematology	X	X	X	X	X	X	X	X	X	X	X	X	X	X	X	
Chemistry	X	X	X	X	X	X	X	X	X	X	X	X	X	X	X	
Coagulation Studies	X	X				X		X					X	X		
HCV, HBV, CMV ⁹	X															
CMV surveillance ¹⁰								X				C6&8	C11, 14, 17 etc			
MRD-PB ¹¹	X											X ²⁶	X ²⁶			
β ₂ -microglobulin	X															
Pregnancy Test ¹³	X					X		X				X	X			
Response Assessments ¹⁴	X											C7	X ¹⁵		X ¹⁶	
Tumor Lysis Risk Assessment ¹⁷		X														
AE Assessment	X	X	X	X	X	X	X	X	X	X	X	X	X	X	X	
Con Meds	X	X	X	X	X	X	X	X	X	X	X	X	X	X	X	
Ublituximab ¹⁸								X	X	X	X	X	X	X	X	
Umbralisib ¹⁹												Daily until confirmed U-MRD				
Cohort A: Ibrutinib ²⁰												Daily until confirmed U-MRD				
Cohort B: Venetoclax ²¹												Dose ramp-up as per package insert and daily until confirmed U-MRD				
Cohort C: Acalabrutinib												Every 12 hours until confirmed U-MRD				

¹ Treatment Administration +/- 1 day window after cycle 1 day 1. Physical Exam, Vital Signs, ECOG PS, Hematology and Serum Chemistry visit days have - 1 day window. All assessments must be completed prior to treatment.

² Treatment Administration +/- 3 day window. Physical Exam, Vital Signs, ECOG PS, Hematology and Serum Chemistry visit days have a - 3 day window during Cycles 2 through 6.

³ Treatment Administration +/- 7 day window. Physical Exam, Vital Signs, ECOG PS, Hematology and Serum Chemistry visit days have a - 7 day window.

⁴ Treatment Administration +/- 3 day window. Physical Exam, Vital Signs, ECOG PS, Hematology and Serum Chemistry visit days have a - 3 day window during Cycles 2 through 6.

⁵ Day 1 every 3 Cycles (Cycle 11, 14, 17, 20, 23, 26): Treatment Administration +/- 7 day window. Physical Exam, Vital Signs, ECOG PS, Hematology and Serum Chemistry visit days have a - 7 day window.

⁶ Cycle 1 Days 8, 15 & 22 assessments only for subjects receiving venetoclax.

⁷ Cycle 2 Day 8 assessments only for subjects receiving venetoclax.

⁸ Vital signs to include temp, BP, HR, respirations and weight (weight only at baseline).

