⁹ Serum Virology to include HBsAg, HBC antibody, HCV antibody, CMV IgG and CMV IgM or CMV by PCR. If HBC antibody is positive, the subject must be evaluated for the presence of HBV DNA by PCR - See Appendix D. If the subject is CMV IgG or CMV IgM positive, the subject must be evaluated for the presence of CMV DNA by PCR.

¹⁰ CMV surveillance by PCR every 3 cycles while receiving study treatment. In addition, a final CMV test by PCR should be done upon treatment discontinuation if not already done within previous 3 months.

¹¹ For retreatment, MRD analysis should be done within 30 days of restarting therapy in peripheral blood (PB) then performed Cycles 6, 8, 11, 14, 17, 20, 23, and 26. If U-MRD in PB during retreatment repeat approximately 4 weeks later. If U-MRD confirmed approximately 4 weeks later, discontinue treatment and follow for progression and survival for 24 months.

¹³ For women of childbearing potential: Serum pregnancy test within 3 days prior to Cycle 1/Day 1; Urine pregnancy tests on Day 1 of each treatment cycle +/- 7 days.

¹⁴ Radiology assessment should include contrasted CT or MRI imaging of neck, chest, abdomen, and pelvis. Scans to be completed within 30 days prior to Cycle 1/Day 1.

¹⁵ Re-treatment subjects – radiology and response assessment within 14 days of Cycles 7, 14, 20, 26 then every 12 months thereafter. At the time of response assessment, bone marrow to be performed as per standard of care if other criteria for complete remission are met. CR should only be confirmed once by bone marrow assessment at planned response assessments.

¹⁶ Response Assessment to be done as per SOC to determine progression-free survival

¹⁷ For subjects being re-treated with venetoclax only. Refer to section 8.3.5.1

¹⁸ Ublituximab Cycle 3 Days 1,2, 8 & 15; Cycle 4-8 Day 1 then every 3 cycles (C11, C14, C17, C20, C23, C26). No further ublituximab after cycle 26

¹⁹ When starting retreatment, dose of umbralisib is at the investigator's discretion, previously tolerated dose should be considered.

²⁰ When starting retreatment, dose of ibrutinib or acalabrutinib is at the investigator's discretion, previously tolerated dose should be considered.

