8.3.6 CRITERIA FOR ONGOING RE-TREATMENT

Continue treatment as per protocol provided the subject has:

- No intolerable toxicities related to study drug.
- D-MRD or has not completed 26 cycles of re-treatment .
- No clinical or radiographic evidence of disease progression.
- Not withdrawn from the study for other reasons.

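### Read literally, the continuation checklist in Section 8.3.6 lets re-treatment run on after confirmed U-MRD alone or after 26 cycles alone, contrary to Section 5.4 and the synopsis, and on confirmed U-MRD contrary to Section 7.3

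*Combined protocol and SAP*

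**What the plan says.** Section 8.3.6 opens with "Continue treatment as per protocol provided the subject has" and then gives four items: no intolerable drug-related toxicity, an MRD and cycle-count item, no disease progression, and no withdrawal for other reasons. The MRD and cycle-count item reads "D-MRD or has not completed 26 cycles of re-treatment".

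Other places state when re-treatment ends:

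- **Section 5.4:** "Retreatment will continue until the occurrence of confirmed U-MRD response in the peripheral blood, completion of 26 cycles (24 cycles of triplet therapy", followed by progression, unacceptable toxicity or withdrawal.
- **Synopsis, re-treatment text:** the same rule, "Retreatment will continue until the occurrence of confirmed U-MRD response in the peripheral blood, completion of 26 cycles (24 cycles of triplet therapy), definitive disease" and so on.
- **Section 7.3, footnote 11:** "If U-MRD confirmed approximately 4 weeks later, discontinue treatment and follow for progression and survival for 24 months".
- **Section 7.3, treatment rows for the oral agents:** "Daily until confirmed U-MRD" for umbralisib and ibrutinib, with equivalent wording for venetoclax and acalabrutinib. No row states a cycle limit.
- **Section 7.3, footnote 18:** "No further ublituximab after cycle 26".
- **Section 8.2:** the re-treatment dosing tables for all three cohorts end at Cycle 26.

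**The concern.** Section 8.3.6 is the list a site would turn to when deciding whether a subject stays on re-treatment. In a list where every item must hold, an item made of two alternatives is met when either one is true. A subject with confirmed U-MRD before Cycle 26 meets it through the cycle count. A subject still D-MRD after Cycle 26 meets it through MRD status. Under 5.4 both subjects would have stopped.

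Two sites following different sections could therefore treat similar subjects for different lengths of time with three drugs. Response, U-MRD rate and PFS on re-treatment form a secondary objective (Section 3.1), and the visible text of Section 11.6.1 gives no re-treatment-specific rule that would deal with such differences.

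Section 8.3.6 also speaks of MRD status without asking for confirmation, whereas 5.4, the synopsis and 7.3 act only on a U-MRD result repeated about 4 weeks later.

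**Working it through.** There is no figure in the plan to reproduce. The check is a comparison of rules, followed by a count of cycles.

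**1. Logic.** Take the other checklist items as met and read D-MRD as not confirmed U-MRD. Section 8.3.6 continues if (D-MRD) or (fewer than 26 cycles completed). Its negation, the condition for stopping, is (U-MRD) and (26 cycles completed). Section 5.4 stops at (confirmed U-MRD) or (26 cycles completed).

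| MRD status | 26 cycles completed? | 8.3.6 as written | 5.4 and synopsis | Agree? |
|---|---|---|---|---|
| D-MRD | No | Continue | Continue | Yes |
| D-MRD | Yes | Continue | Stop | No |
| Confirmed U-MRD | No | Continue | Stop | No |
| Confirmed U-MRD | Yes | Stop | Stop | Yes |

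The rules agree in 2 of 4 states.

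**2. Where Section 7.3 stands.** In the third row, footnote 11 sides with 5.4: confirmed U-MRD ends treatment. In the second row, 7.3 is explicit only for ublituximab (footnote 18). Its oral-agent rows name confirmed U-MRD as the end and give no cycle limit, so they do not contradict 8.3.6 there.

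**3. Confirmation.** Before Cycle 26 is completed, the cycle-count alternative alone satisfies the 8.3.6 item, so the missing qualifier has no effect on the literal reading. It matters once 26 cycles are done. If U-MRD is first seen at Cycle 26, the repeat test falls after that cycle, and 8.3.6 does not say whether such a subject counts as D-MRD meanwhile.

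**4. Largest difference in exposure (third row).** Inputs: re-treatment MRD tests in Cycles 6, 8, 11, 14, 17, 20, 23 and 26 (7.3, footnote 11); ublituximab on Day 1 of Cycles 4 to 8, then Cycles 11, 14, 17, 20, 23 and 26 (7.3, footnote 18); 28-day cycles. Assumptions: confirmation falls in the next cycle, and that cycle is completed. The second is stated for initial treatment (7.1, footnote 11) but not for re-treatment.

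If U-MRD is first found in Cycle t, the cycles remaining after Cycle t + 1 number 26 − (t + 1) = 25 − t.

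| First U-MRD (t) | Further cycles | Days (× 28) | Further ublituximab infusions |
|---|---|---|---|
| 6 | 19 | 532 | 7 (Cycles 8, 11, 14, 17, 20, 23, 26) |
| 8 | 17 | 476 | 6 |
| 11 | 14 | 392 | 5 |
| 14 | 11 | 308 | 4 |
| 17 | 8 | 224 | 3 |
| 20 | 5 | 140 | 2 |
| 23 | 2 | 56 | 1 |

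The first line is the maximum, for the earliest responder. The documents give no distribution of response times on re-treatment, so no average can be computed.

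**The case against.** The strongest reply is that this is a one-word drafting slip which no site would act on. The lead-in ties continuation to the protocol, so the list can be read as adding conditions to the rules elsewhere rather than replacing them. Section 5.4, the synopsis and footnote 11 are all clear on confirmed U-MRD. The exposure figures require a site to follow one item and disregard those three places. A slip is indeed likely, and the figures are a worst case. But nothing in 8.3.6 corrects its own wording, I found no clause giving one section precedence, and this is the section headed as the criteria for ongoing re-treatment. The contradiction stands.

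Three stronger readings are tempting, and the documents do not support them.

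- **That D-MRD subjects would be treated without end.** Section 8.3.6 itself sets no ceiling for them, but the 8.2 dosing tables and the scheduled MRD tests end at Cycle 26 and ublituximab stops there. No dosing schedule is laid out beyond that point.
- **That all of 7.3 contradicts 8.3.6 on both events.** It does so on confirmed U-MRD. On the 26-cycle limit it does so only for ublituximab.
- **That the U-MRD results are distorted.** A subject who continues after confirmed U-MRD is already a responder, and a D-MRD subject past Cycle 26 has no further scheduled MRD test, so the re-treatment U-MRD rate barely moves. Mixed on- and off-treatment follow-up in PFS already arises under 5.4, because subjects stop at different times; 8.3.6 can add only variation between sites.

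**Conclusion.** The inconsistency is real and should be corrected. As written, 8.3.6 conflicts with 5.4 and the synopsis in two of four states, and with footnote 11 of 7.3 in one of them (confirmed U-MRD before 26 cycles). For D-MRD after 26 cycles, 7.3 conflicts explicitly only through the ublituximab limit.

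The consequence is possible extra exposure and uneven re-treatment follow-up across sites. The ceiling in the confirmed U-MRD case is 19 cycles and 7 infusions, under the timing assumptions above and only if a site applies 8.3.6 literally. It concerns the subset who progress after 6 months of treatment-free observation and are re-treated. The primary endpoint is assessed during Cycles 3 to 24 of initial treatment (Section 11.6.1.1) and is not affected. No view is taken here on which stopping rule is clinically right.

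**What to change.** Reconcile 8.3.6, 5.4, the synopsis and 7.3 (the oral-agent rows and footnotes 11 and 18) so that a single stopping rule for re-treatment, chosen by the sponsor, is stated identically in each place. Say explicitly how MRD status and cycle count combine and whether the cycle limit covers the oral agents as well as ublituximab. Use the same wording on confirmation of U-MRD throughout, including for a result still awaiting its repeat test.

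The cost is a few lines of text, handled through the amendment process in Section 15.3. The wording correction itself needs no added assessments or subjects.

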8.4 DOSING DELAYS AND MODIFICATIONS

Subjects should be assessed clinically for toxicity at each visit using the NCI CTCAE v5.0 ([https://ctep.cancer.gov/protocoldevelopment/electronic_applications/docs/CTCAE v5 Quick Reference 8.5x11.pdf](https://ctep.cancer.gov/protocoldevelopment/electronic_applications/docs/CTCAE_v5_Quick_Reference_8.5x11.pdf)) grading scale. Dose delay and/or modification guidance is for adverse events considered at least possibly related to the study drug. If cytopenias are deemed related to the underlying disease rather than study drug, dose modifications are not required but may be carried out per investigator discretion.

Delay of treatment is allowed for recovery of toxicities. Please contact TG Therapeutics with any questions prior to re-initiating treatment after extended drug holds. If there is a dose modification for the oral agents, the subject should be notified of the change in dose and the

appropriate staff should instruct the subject about the revised number of study medication tablets to be used per dose according to the new dose level.

In the case of drug discontinuation, subjects will be followed for disease progression.

8.4.1 DOSE DELAY: UBLITUXIMAB

No reduction in the dose of ublituximab is permitted. Please refer to 'Guidelines for Administration of Ublituximab' for detailed information on infusion rate guidance for infusion related reactions related to ublituximab.

Supportive care should be considered for any subject who experiences Grade ≥ 2 cytopenias or Grade ≥ 1 non-hematologic toxicities.

If a subject discontinues only one study drug, the subject may continue treatment with the other study drug(s) per the protocol.

If Grade 4 anaphylaxis is observed at any point during ublituximab treatment, permanently discontinue ublituximab treatment and intervene as per investigator discretion.

TABLE 2: DOSE DELAY GUIDELINES: UBLITUXIMAB

NCI-CTCAE Grade	Dose Delay and/or Modification
Hematologic Adverse Event	
Neutropenia	
Grade ≤ 3 neutropenia	Maintain current dose. Consider supportive care as warranted.
Grade 4 neutropenia or occurrence of neutropenic fever or infection	Delay ublituximab until Grade ≤ 3 and/or neutropenic fever or infection is resolved; consider growth-factor support as warranted; thereafter, resume at full dose.
Thrombocytopenia	
Grade ≤ 3 thrombocytopenia	Maintain current dose level and provide supportive care as clinically warranted.
Grade 4 thrombocytopenia	Delay ublituximab until Grade ≤ 3 ; consider intervention with supportive care as warranted; thereafter resume at full dose.
Non-Hematological Adverse Events	
Grade ≤ 2	Maintain current dose level
Grade ≥ 3	Withhold ublituximab until Grade ≤ 2 at the discretion of the investigator; consider supportive care intervention as warranted. Resume at full dose.

8.4.2 DOSE DELAY/MODIFICATIONS: UMBRALISIB

Supportive care should be considered for any subject who experiences Grade ≥ 2 cytopenias, or Grade ≥ 1 non-hematologic toxicities.

If a subject discontinues one study drug, the subject may continue treatment with the other study drug(s) per the protocol.

TABLE 3: UMBRALISIB DOSE DELAY AND/OR MODIFICATIONS GUIDANCE

NCI-CTCAE Grade	Dose Delay and/or Modification
Hematologic Adverse Event	
Neutropenia	
Grade \leq 2 neutropenia	Maintain current dose. Consider supportive care as warranted.
Grade 3 neutropenia	Maintain current dose, consider supportive care. If recurrence or persistent Grade 3, consider reducing umbralisib to next lower dose level or maintain current umbralisib dose at discretion of the investigator.
Grade 4 neutropenia or occurrence of neutropenic fever or infection	Delay umbralisib until Grade \leq 3 and/or neutropenic fever or infection is resolved; thereafter, resume at full dose. Consider supportive care. If recurrence after re-challenge, delay umbralisib until Grade \leq 3 and/or neutropenic fever or infection is resolved; thereafter, resume umbralisib at current dose or at next lower dose level at discretion of the investigator.
Thrombocytopenia	
Grade \leq 3 thrombocytopenia	Maintain current dose level and provide supportive care as clinically warranted.
Grade 4 thrombocytopenia	Delay umbralisib until Grade \leq 3; thereafter, resume at full dose. Consider supportive care intervention as warranted. If recurrence after re-challenge, delay umbralisib until Grade \leq 3; thereafter resume umbralisib at current dose or at next lower dose level at discretion of the investigator.
Pulmonary & Related Infections*	
Grade 1 & 2	Stop all therapy and hold until complete resolution. Restart umbralisib at one lower dose level. Restart ublituximab (if applicable) at full dose. If recurrence after re-challenge, discontinue all treatment therapy.
Grade \geq 3	Discontinue all therapy
For sinopulmonary infections clearly not related to immune-mediated pneumonitis, umbralisib may be continued at investigator's discretion. While pneumonitis has been minimal with umbralisib, it is a reported adverse event associated with other PI3K delta inhibitors. Use of anti-pneumocystis and anti-herpetic viral prophylaxis is required for subjects receiving umbralisib.	
Diarrhea and/or Colitis	
Diarrhea Grade \leq 2	Maintain current dose level if tolerable or hold and then resume at current dose level once has resolved. NOTE: If persistent grade 2 diarrhea, despite supportive care, delay umbralisib until \leq grade 1. If recurrence after re-challenge, resume at full dose or next lower dose level at discretion of the investigator.
Diarrhea Grade \geq 3	Withhold umbralisib until Grade \leq 2. Resume at full dose or next lower dose level as per discretion of investigator If recurrence after re-challenge, resume at next lower dose level at discretion of the investigator.
Colitis (all Grades)	Hold umbralisib. Treat with supportive care and after resolution of colitis, resume umbralisib at next lower dose level
Liver Toxicity (ALT/SGPT, AST/SGOT, Bilirubin, Alkaline Phosphatase)	
Grade 1	Maintain current umbralisib dose. Assess concomitant medications and risk factors*. Monitor labs every 1-2 weeks.
Grade 2	Maintain current umbralisib dose. Assess concomitant medications and risk factors*. Begin supportive care (prednisone 0.5-1.0 mg/kg/day or equivalent per investigator discretion) **. Monitor labs at least weekly until Grade 1.

	
Once resolved to Grade ≤1, taper prednisone by 10 mg per week until off.
 
If liver toxicity recurs to Grade 2:
 
 ○ Re-initiate steroids. ○ Monitor labs at least weekly until Grade 1. ○ Consider delaying umbralisib. ○ Once resolved to Grade ≤1 
 ○ If umbralisib was delayed, restart umbralisib at current dose. ○ Taper prednisone by 10 mg per week until off.
Grade ≥3	
Delay umbralisib.
 
Assess concomitant medications and risk factors*.
 
Begin/continue supportive care (prednisone 0.5-1.0 mg/kg/day or equivalent per investigator discretion) **.
 
Monitor labs at least weekly until Grade 1.
 
Once resolved to Grade ≤1:
 
 ○ Restart umbralisib at one lower dose level. ○ Taper prednisone by 10 mg per week until off.

* Assess for disorders of lipids and glucose, thyroid disorders, alcohol use, viral infections, etc.
 
**Supportive Care – Aggressive management of lipid, glucose, other metabolic disorders, viral infections, etc.
 
Important: Before initiating steroids, check for viral hepatitis or CMV infection.
	
All Other Non-Hematological Adverse Events	
Grade ≤2	Maintain current dose level
Grade ≥3	
Withhold umbralisib until Grade ≤2.
 
If recurrence after re-challenge, delay umbralisib until Grade ≤ 2; thereafter resume umbralisib at current dose or at next lower dose level at discretion of the investigator.

TABLE 4: STUDY DRUG DOSE LEVELS

Study Drug	Starting Dose	1 st Dose Reduction	2 nd Dose Reduction
Umbralisib	800 mg	600 mg	400 mg

A maximum of two dose level reductions are allowed for umbralisib. If a subject requires a dose reduction of umbralisib due to study drug related toxicity, the dose may not be re-escalated. If further evaluation of the toxicity reveals the event was not related to umbralisib, this must be recorded in the medical record and dose re-escalation to the next higher dose level may be considered at the discretion of the investigator.

